1.0 Study Summary

Study Title	A Randomized Controlled Trial of an Exposure-Based Intervention for Perfectionism
Study Design	Randomized Intervention Trial
Primary Objective	Evaluate the efficacy of an exposure-based intervention for perfectionism.
Secondary Objective(s)	Evaluate the effect of the intervention on depressive, anxiety, and eating disorder symptoms.
Research Intervention(s)	Exposure-Based Intervention for Perfectionism (see details below)
Study Population	FSU student subject pool participants and community participants
Sample Size	84
Study Duration for individual participants	6 weeks
Study Specific Abbreviations/ Definitions	Exposure-based intervention for perfectionism (ETP)

2.0 Objectives*

2.1 The purpose of this study is to test the efficacy of an exposure-based intervention for perfectionism. The aims of the study include:

- Evaluating whether a short-term computerized intervention can decrease perfectionism symptomatology (as measured by the Frost Multidimensional Perfectionism Scale (FMPS)).
- Seeing if this intervention also decreases levels of anxiety, depression, and symptoms of eating disorders.

2.2 We hypothesize that the exposure-based intervention for perfectionism (ETP) group will have significantly lower levels of perfectionism than the stress management group at post-test and follow-up. We also hypothesize that the ETP group will have decreased levels of anxiety, depression, and eating disorder symptoms at post-test and follow-up than those in the stress management group, after controlling for baseline scores.

3.0 Background*

3.1 Perfectionism is a transdiagnostic concept that has been conceptualized as multidimensional. Frost et al. (1990) indicated that there were five dimensions of perfectionism including (1) concern over mistakes, (2) personal standards, (3) doubts about actions, (4) parental expectations, (5) parental criticism, and (6) organization. Similarly, Hewitt and Flett (1990) also reported that perfectionism is multidimensional and includes self-oriented, other-oriented, and socially prescribed perfectionism. A recent review of these conceptualizations showed that they continue to be accurate and relevant (Smith et al., in press).

Perfectionism has been associated with depression, anxiety, eating disorders, obsessive-compulsive disorder, and personality disorders, making it a transdiagnostic concept (Dimaggio et al., 2015; Egan et al., 2011; Fairburn et al., 2003; Limburg et al., 2017). Perfectionism is an important target for intervention as it spans many different disorders and has a negative impact on intervention outcome. Higher levels of perfectionism have been found in individuals with anorexia or bulimia nervosa than in controls (Sassaroli et al., 2008). Bardone-Cone et al. (2007) suggested that repeatedly attempting to hide mistakes may lead those high in perfectionism to develop an eating disorder.

In addition, poor intervention response has been predicted by high levels of perfectionism (Bizuel et al., 2001; Blatt, 1995; Blatt et al., 1998; Elkin et al., 1989; Shahar et al., 2004; Zuroff et al., 2000). More specifically, Blatt (1995) found that heightened perfectionism interfered with intervention for depression. In those with anorexia nervosa, perfectionism contributed to intervention resistance, drop out, and relapse (Bastani et al., 1995; Sutandar-Pinnock et al., 2003).

Several interventions for maladaptive perfectionism have been developed, including face to face and self-guided interventions. Cognitive behavioral therapy (CBT) has been the most commonly evaluated intervention for perfectionism thus far. A recent meta-analysis reviewed the efficacy of cognitive behavioral therapy (CBT) for perfectionism, including 15 randomized-controlled trials

PROTOCOL TITLE: A Randomized Controlled Trial of an Exposure-Based Intervention for Perfectionism

that included waitlist, placebo, and active control groups (Galloway et al., 2021). They found that CBT for perfectionism is efficacious with medium to large effect sizes reported for personal standards, concern over mistakes, and clinical perfectionism. Furthermore, medium effect sizes were reported for eating disorders and depression, and small-medium effect sizes were reported for anxiety. Additionally, a meta-analytic review of perfectionism intervention research had similar findings including significant reductions in perfectionism when compared to waitlist, general stress management, self-help, and a CBT-based general psychology group (Suh et al., 2019). Lloyd et al. (2015) also completed a meta-analytic examination of CBT for perfectionism and found that CBT, both in person and online, outperformed waitlist, self-help, and stress management control conditions with medium to large effect sizes. Decreases in depression and anxiety were also found post-intervention (Lloyd et al., 2015; Suh et al., 2019).

Though exposures have been used within cognitive behavioral therapy, only one intervention study thus far has focused on an intervention focusing completely on exposures ([name] & [name], under review). The exposure-based intervention for perfectionism (ETP) included several tasks designed to elicit accidental and intentional mistake-making to target elevated levels of concern over mistakes. These tasks were completed by undergraduate participants during five intervention sessions for two weeks (one session every three days). Compared to waitlist, ETP significantly decreased levels of overall perfectionism, concern over mistakes, levels of depression and social anxiety, and eating disorder symptoms. Effect sizes were comparable to previously evaluated longer interventions (e.g., 6 to 12 weeks of cognitive behavioral therapy for perfectionism).

3.2 The knowledge gained from this study will add to the existing literature by obtaining information about a computerized intervention for perfectionism. We would like to further research on ETP by comparing it to a stress management condition and observing if the effects remain one month after the intervention has been completed.

4.0 Study Endpoints*

- 4.1 The primary endpoint will be scores from the Frost Multi-Dimensional Perfectionism Scale (FMPS)- Concern Over Mistakes Subscale at post-test. We will evaluate pre vs. post differences. The secondary endpoint will include scores from the Center for Epidemiological Studies Depression Scale (CES-D), the Generalized Anxiety Disorder-7 (GAD-7), the Social Phobia Inventory (SPIN), and the ED-15 to see if there are any decreases from pre to post assessment.
- 4.2 Additionally, we will evaluate post-test versus one month follow-up differences on the above stated measures.

5.0 Study Intervention

- 5.1 Description: Exposure-Based Perfectionism Intervention (EPT) involves repeated engagement in computerized tasks that instruct participants to purposefully make mistakes. There are three main tasks:

Shape Ordering Task: The first task presents participants with a series of shapes followed by a question asking in which order they saw the shapes. They have 20 seconds to decide in which order the shapes were presented. The task begins by showing three shapes and then

PROTOCOL TITLE: A Randomized Controlled Trial of an Exposure-Based Intervention for Perfectionism

asking their order and increases to eight shapes. Participants automatically advance after the 20 seconds they are given to decided. A feedback screen then appears with correct or incorrect based on their responses.

Spelling Task: Participants are instructed to read a sentence then type the sentence in a textbox below misspelling three words. The screen immediately following displays their sentence with the spelling errors and tells participants to read the sentence. After 10 seconds, they are automatically advanced to a feedback screen that displays “incorrect”.

Math Task: Simple math problems (e.g., addition, subtraction, multiplication, and division) are displayed to participants. Some of the math problems include both correct and incorrect answers while others only include incorrect answers, with participants actively choosing an incorrect answer to proceed in the task. For questions with both correct and incorrect answers, a “correct” or “incorrect” screen appears based on their response. For questions with only incorrect answers, a feedback screen appears with “incorrect”.

6.0 Procedures Involved*

6.1 The study will be a randomized control design, with 50% of participants receiving the ETP and 50% of subjects receiving the stress management condition.

- The stress management condition will consist of psychoeducational videos about exercise, diet, hygiene, social support, and sleep. This will be followed by relaxing videos of the rainforest, wildlife, or space. This condition is based on previous studies run by our lab, including [name] et al. (2017).

6.2 Participants will be identified using the mass screening survey distributed to the pool of psychology students maintained by the psychology department (SONA) or using a brief, 3 question screener that includes three questions from the FMPS-CM. Participants who score a 9 or higher on the screener will be invited to participate in the current study and be provided with the study passcode to sign up if they are interested.

Once they sign up, all participants will be emailed a link to the informed consent form, which will be administered using a Qualtrics survey. All participants must first complete the informed consent before beginning other study procedures. After consenting, the participant will be directed to complete the FMPS and questions to assess exclusion criteria. If the participant scores a 28 or lower on the FMPS-CM or do not meet all inclusion, they will be given credit for their time (.5 credits) and the experiment will end.

In addition to student participants recruited via the mass screener and SONA, participants from the community will be provided the opportunity to participate for monetary compensation in the form of Amazon gift cards, which will be sent to them via email. Community participants will be given a link to the informed consent form before beginning study procedures. After consenting, community participants will be directed to complete the FMPS and questions to assess exclusion criteria. If they score lower than 29 on the FMPS-CM or meet any

PROTOCOL TITLE: A Randomized Controlled Trial of an Exposure-Based Intervention for Perfectionism

exclusionary criteria, they will be told they do not qualify for the study and will not be compensated.

If participants meet inclusion criteria, they will be randomized to either the exposure-based perfectionism intervention (ETP) group or the stress management group. Based on that randomization, they will be sent one of two Qualtrics links:

1. Stress Management Condition Qualtrics Link: This link will include questionnaires asking about their perfectionism, mood, and behaviors. A detailed list of questionnaires is provided below. After completing questionnaires, participants will be directed to a screen explaining that they will watch a series of videos educating them on health behaviors, including exercise, diet, sleep, and social support, and will then watch relaxing videos about nature. They will also be informed that they will be asked to click on a link to complete the first session immediately following this video and complete the sessions at home 7 times: 2, 4, 6, 8, 10, 12, and 14 days after the baseline visit. A Qualtrics link to the first session will be provided on the page after this explanation. At the end of the session, they will be directed to a screen reminding them that they will receive Qualtrics links 7 more times over the next two weeks: 2, 4, 6, 8, 12, and 14 days after the baseline visit. They will be instructed to complete each intervention session within 24 hours of receiving the link.

2. ETP Qualtrics Link: This link will include questionnaires asking about their perfectionism, mood, and behaviors. A detailed list of questionnaires is provided below. After completing questionnaires, participants will be directed to a screen providing information about perfectionism and the rationale of the intervention. They will also be informed that they will be asked to click on a link to complete the first intervention session immediately following this video and complete the intervention at home 7 more times: 2, 4, 6, 8, 10, 12, and 14 days after the baseline visit. A Qualtrics link to the first intervention session will be provided on the following page.

They will then complete the first intervention session using the provided link. This will include three tasks, each targeting specific symptoms of perfectionism. Detailed information about the tasks is provided above. At the end of the intervention session, they will be directed to watch a video reminding them that they will receive Qualtrics links 7 more times over the next two weeks: 2, 4, 6, 8, 12, and 14 days after the intervention. They will be instructed to complete each intervention session within 24 hours of receiving the link.

Sixteen days after the baseline visit, participants in both groups will be asked to complete the post-assessment questionnaires via a link that will be sent to them via email. One month after completing the post-test measures, they will be sent the same questionnaires to complete again. SONA participants will receive 3 credits after completing the post-test questionnaires and 1 credit after completing the follow-up questionnaires. Community participants will receive an Amazon gift card via email for \$10 after completing the post-test questionnaires and an additional Amazon gift card, delivered via email, for \$10 after completing the follow-up questionnaires.

PROTOCOL TITLE: A Randomized Controlled Trial of an Exposure-Based Intervention for Perfectionism

All participants will be debriefed after completing follow-up assessments.

After completing all assessments for the study, participants will be emailed to ask for feedback about the treatment. The text of the email will say:

“We are interested in your feedback on the treatment for perfectionism you received. What were your general impressions of the treatment? Were there parts of the treatment you would change to make it better? If so, what would you recommend?”

They may opt-out or not reply if they choose.

Questionnaires:

Frost Multidimensional Perfectionism Scale (FMPS; Frost et al., 1990)

Credibility and Expectancy Questionnaire (Borkovec & Nau, 1972)

Center for Epidemiological Studies Depression Scale (CES-D; Radloff, 1977)

Social Phobia Index (SPIN; Connor et al., 2000)

Generalized Anxiety Disorder-7 (GAD-7; Spitzer et al., 2006)

ED-15 (Tatham et al., 2015)

Irrational Procrastination Scale (IPS; Steel, 2010)

Massachusetts General Hospital Hair Pulling Scale (MGH-HPS; Keuthen et al., 1995)

Skin Picking Scale Revised (SPS-R; Snorrason et al., 2012)

6.3

- Participants who have previously completed ETP reported no adverse effects ([name] & [name], under review).
- To lessen the risks, participants will be explained what the conditions will look like and what the rationale behind it is before engaging in interventions.
- All data collection materials can be found in the appendix of the IRB submission.

6.4 Data collected during the study will be obtained via self-report from subjects. Data will include demographics and self-report questionnaire responses.

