14.0 Withdrawal of Subjects*

- 14.1* Subjects may be withdrawn from the study without their consent if a risk arises that could harm the participant or others. For example, if a subject discloses intent to harm themselves or others, they may be withdrawn from the study.
- 14.2* When subjects withdraw from the research before the completion of the study, we will ask if they are willing to complete the post-test assessment.

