15.0 Risks to Subjects*

- 15.1* The risks to human subjects in the proposed study are minimal. Nevertheless, precautions will be taken to minimize participants' risk in the study. All individuals will be informed of the nature of the investigation and the types of assessments and procedures. Participants will be given an opportunity to have any questions answered to their satisfaction and then will be asked to sign an informed consent statement prior to participating in the project. The specific potential risks involved in the proposed investigation are enumerated below.

PROTOCOL TITLE: A Randomized Controlled Trial of an Exposure-Based Intervention for Perfectionism

Self-report measures:

There are no foreseeable risks associated with these assessment procedures. While some participants may be hesitant to answer the assessment forms, others may derive benefit from the self-assessment as it could increase their awareness of the relationship between their symptoms and environmental, cognitive, and interpersonal factors. In addition, referrals to appropriate clinical services (e.g., ABHC, FSU Psychology Clinic) will be provided for any participants seeking intervention after the study. Phone numbers for these clinical services will be provided within the debriefing form, which will be available for participants to read on Qualtrics after completing the follow-up questionnaires.

Intervention risks:

The perfectionism intervention is exposure-based, which means that it is expected to involve some discomfort for the subject. The intervention may lead to distress for subjects. They are told that they may feel psychologically uncomfortable, but that it is expected during this intervention. Participants will be able to stop intervention at any time. The benefits of exposure-based interventions have shown that though anxiety-provoking, the distress is temporary and there is often symptom-relief both in the short and long-term. For the stress management condition, similar tasks have been used in previous research ([name] et al., 2017; Smith et al., 2018; Smith et al., 2019) and are very unlikely to cause any significant distress or discomfort.

General Protection Against Risks:

At their request, participants will be referred to clinicians with whom they may speak about their discomfort or distress.

Safeguards for maintaining confidentiality:

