17.0 Data Management* and Confidentiality

17.1 The data analysis plan begins with univariate and multivariate outliers being identified and transformed via Winsorization (Tukey & McLaughlin, 1963). Skewness and kurtosis will also be evaluated. Baseline differences between groups will then be identified using Chi-squared tests and independent samples t-tests. To analyze main outcomes, hierarchical intent-to-treat regression models will be used. These models will control for baseline variables. Multiple imputation using 20 iterations will be used to account for missing data. Effect sizes will be calculated using R^2 change values and were interpreted using Cohen's guidelines: small = .01, medium = .09, large = .25 (Cohen, 1988).

Secondary analyses include intervention response on measures of depression, trait anxiety, social anxiety, and eating disorder symptoms. Baseline values will be covaried in the regression models.

17.2 The data will be password protected on an encrypted computer only accessible by the research team. All identifying information will be removed and subjects will be referred to by ID numbers. Consent forms that include subjects' names will be stored on an encrypted computer only accessible to the research staff.

17.3 How data will be handled:

- Information in the data will include an ID number, demographics and all self-report assessment responses.
- Data will be stored in password-protected files on an encrypted computer that only the study team has access to.
- Data will be stored for a minimum of 4 years after study completion.
- Only members of the study team (i.e., those listed on the IRB submission) will have access to the data.
- The investigator is responsible for receipt or transmission of the data.
- If data needs to be transported, it will be done via password protected files on encrypted computers.

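### No follow-up link is scheduled for people who miss post-test, and withdrawers are not asked for follow-up, so obtainable one-month scores may be left to imputation

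*Combined protocol and SAP*

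**What the plan says.** Section 6.2 sends post-test to both groups sixteen days after baseline. It then gives the only operational rule for follow-up: "One month after completing the post-test measures, they will be sent the same questionnaires to complete again". For people who leave the study, section 14.2 says "we will ask if they are willing to complete the post-test assessment" and does not mention follow-up.

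Follow-up carries weight in the plan. Section 2.2 predicts that the ETP group "will have significantly lower levels of perfectionism than the stress management group at post-test and follow-up". Section 4.2 adds that "we will evaluate post-test versus one month follow-up differences on the above stated measures". Section 3.2 gives as a reason for the trial "observing if the effects remain one month after the intervention has been completed".

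Section 17.1 specifies intent-to-treat regression models with baseline as a covariate. On missing values it says "Multiple imputation using 20 iterations will be used to account for missing data". It names no time point, so applying it to follow-up is an inference, though the natural one.

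**The concern.** Two groups have no stated follow-up collection rule. The first is people who never complete post-test, whether or not they formally withdraw: the clock in section 6.2 never starts for them. The second is people who complete post-test and then withdraw: section 14.2 asks them for nothing further.

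Anyone building an automated email schedule from this text has no date for the first group and no instruction for the second. Some of these people might have answered. If they are not asked, their follow-up scores are imputed, and for the first group the imputation has only baseline to work from. A follow-up score not collected on time cannot be collected later.

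The loss need not be equal in the two arms. Section 15.1 says of ETP that "The intervention may lead to distress for subjects", and of the stress management tasks that they "are very unlikely to cause any significant distress or discomfort". That makes unequal dropout plausible, but does not show that it will happen.

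**Working it through.** **1. Who is covered by the text**

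| Participant | Post-test requested? | Follow-up requested? |
|---|---|---|
| Stops sessions, completes post-test | Yes (6.2, day 16) | Yes (6.2) |
| Withdraws, agrees to post-test and completes it | Yes (14.2) | Can be read as yes, through 6.2 |
| Skips post-test without withdrawing | Yes (6.2) | No date given |
| Withdraws and declines post-test | Yes (14.2) | No date given, not asked |
| Completes post-test, then withdraws | Already done | Not asked (14.2) |

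The last three rows are the gap.

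**2. Does another section supply a date?** Taking a month as 30 days:
- Section 6.2: day 16 + 30 = day 46, or later if post-test is completed late.
- Section 3.2, one month after the intervention, with the last session on day 14: 14 + 30 = day 44.
- Study Summary and section 9.1, six weeks in total: 6 × 7 = day 42.

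These agree on an approximate timing. None of them schedules a link, and none changes 14.2.

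**3. How many scores?** The documents give no dropout rate. Section 25.1 needs 68 and recruits up to 80, which implies an allowance of 1 − 68/80 = 15.0%. Against the 84 in section 12.1, it is 1 − 68/84 = 19.0%. As an illustration, assume 6 of 42 per arm miss post-test (12/84 = 14%) and there is no other loss:
- as written: 84 − 12 = 72 observed follow-up scores;
- 1 of 6 per arm answers: 72 + 2 = 74;
- 3 of 6 per arm answer: 72 + 6 = 78;
- nobody answers: 72.

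Over a wider assumed range (10% to 30% miss post-test, 25% to 50% of those answer), the gain runs from 84 × 0.10 × 0.25 = 2.1 to 84 × 0.30 × 0.50 = 12.6 people.

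**4. Precision.** Simulation with 42 per arm and these assumptions: true effect 0.60 SD at both times; correlations 0.5 (baseline with post-test), 0.5 (baseline with follow-up) and 0.7 (post-test with follow-up); 6 per arm missing post-test, related to outcome in the ETP arm only; 20 imputations by chained regressions on arm, baseline and the other time point; analysis of follow-up on arm and baseline. The mean standard error is 0.206 at 72 observed, 0.204 at 74 and 0.198 at 78. The reduction is 0.002/0.206 = 1.0% to 0.008/0.206 = 3.9%.

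**5. Bias.** Same kind of simulation, follow-up effect in SD, with dropout related to outcome in ETP only:

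| Who returns | Full data | None returns | 1 of 6 per arm | 3 of 6 per arm |
|---|---|---|---|---|
| Dropouts at random | 0.603 | 0.666 | 0.655 | 0.628 |
| Best-faring ETP dropouts | 0.602 | 0.666 | 0.680 | 0.673 |

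In the first row the estimate moves towards the full-data value; in the second it moves slightly away. When dropout is related to outcome equally in both arms (full 0.594, imputed 0.590), or to baseline only (0.589 and 0.588), there is no bias to remove. The last two pairs assume a further 4 per arm lost at follow-up.

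**6. What was not sized.** No simulated case recovers people who withdraw after post-test, so the change to 14.2 has no computed gain for them.

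**The case against.** The best reply is that section 6.2 states timing for the ordinary case. It contains no condition restricting follow-up to post-test completers, and the same section has all participants debriefed after follow-up, which treats follow-up as universal. Sections 3.2 and 9.1 give staff a rough date. The staff checklist mentioned in 25.1 and the consent form are not in the text reviewed and may hold a sending rule.

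Much of this stands. A reader might infer that the plan excludes these people from follow-up, or will lose every score they would have given. The documents do not support that: they are silent, and staff may send the link anyway. What remains is that no instruction tells them to, and 14.2 lists post-test alone.

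A reader might also infer that the follow-up effect will be overstated by some known percentage. The documents give no dropout rate or mechanism. An overstatement appears in the simulation only after assuming outcome-related dropout that differs between arms, and that assumption, not this gap, is its source. Section 15.1 also calls the risks minimal and the distress temporary, and section 6.3 reports no adverse effects among people who previously completed ETP.

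Finally, someone without a post-test supplies no observed pair for the comparison in 4.2. That is correct. For that group the gain is in the between-arm follow-up comparison of section 2.2. People who withdraw after post-test would supply a pair.

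**Conclusion.** The gap is real and modest. Post-test non-completers have no scheduled follow-up link, and people who withdraw after post-test are not asked for follow-up, although follow-up belongs to the hypotheses and endpoints and the models are intent-to-treat.

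The expected gain from closing it is more observed follow-up data and slightly better precision: 2 to 6 more scores of 84 and a standard error 1% to 4% smaller in the main illustration, and nothing if nobody responds. These figures rest on an assumed dropout rate, response rate, effect size and correlations.

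Reduced bias should not be claimed as a benefit, because it depends on who returns. Nor does the gap undermine the primary analysis: that endpoint is at post-test (4.1), and a recovered follow-up score bears on it only by informing the imputation of a missed post-test. The case for acting is that the change is cheap and has to be made before the scores fall due.

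**What to change.** - In 6.2, send the follow-up link to every randomized participant who has not refused further contact, whatever sessions or post-test they completed.
- Keep one month after post-test for those who complete it. Set a closing date for post-test. For those who have not completed it by then, use a default follow-up date one month after the day-16 due date (about day 46). The closing date prevents a late completer from having two follow-up dates.
- In 14.2, ask withdrawers for both post-test and follow-up.
- In 17.1, state that the imputation model includes both time points, so that a recovered follow-up score is used.

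The cost is one more rule in the email schedule, one sentence in 14.2, and the existing follow-up payment of $10 (community) or 1 SONA credit (students) per extra responder. If all were paid in gift cards, that is 2 × $10 = $20 to 6 × $10 = $60 in the illustration, and at most 12 × $10 = $120 if all twelve respond.
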